When people who do not speak English are excluded from participation in the research, provide the scientific rationale for doing so. Individuals who do not speak English should not be denied participation in research simply because it is inconvenient to translate the consent form in different languages and to have an interpreter present.

The interpreting services and the “Short Form” consent forms will be utilized to enroll any subjects who wishes to participate but does not speak English. We will provide a translator obtained from interpreter services department who is fluent in English and the subjects’ native language

For guidance, refer to the following Partners policy:

Obtaining and Documenting Informed Consent of Subjects who do not Speak English
<http://healthcare.partners.org/phsirb/nonengco.htm>

RECRUITMENT PROCEDURES

Explain in detail the specific methodology that will be used to recruit subjects. Specifically address how, when, where and by whom subjects will be identified and approached about participation. Include any specific recruitment methods used to enhance recruitment of women and minorities.

Subjects will be recruited from our database of existing research subjects. Subjects also may be recruited through word of mouth, email, telephone, newspaper, internet and social media sites such as Facebook and Craigslist, and or bulletin fliers. Should the subject be interested in the study, they can call or email the study physician or coordinator to inquire about study participation. All email sent outside of the Partners firewall containing confidential information will be encrypted using "Send Secure" as per policy. Subjects may opt out of encrypted email communications if they have been advised of the risks associated with unencrypted email, and they indicate a preference to receive unencrypted email despite the risks.

Only patients who have stated in the initial clinical questionnaire that they are interested in hearing about research studies will be contacted by phone or email. During the phone or email interview patients will first be asked if they are willing to hear about research studies. If they aren't, the interview will be stopped. Patients will be called or emailed by one of our technicians who are not treating patients at the outpatient clinic. Therefore, patients won't feel obliged to participate because of a therapeutic relationship.

Individuals who respond and are interested in participating in this study will be given a thorough review of the risks, discomforts, potential benefits and their expected involvement during the initial phone or email conversation. Both men and women and people of all racial and ethnic backgrounds will be studied.

Provide details of remuneration, when applicable. Even when subjects may derive medical benefit from participation, it is often the case that extra hospital visits, meals at the hospital, parking fees or other inconveniences will result in additional out-of-pocket expenses related to study participation. Investigators may wish to consider providing reimbursement for such expenses when funding is available

Subjects will receive \$100/night for participation in this study. Compensation for parking costs or taxi vouchers will also be provided

For guidance, refer to the following Partners policies:
Recruitment of Research Subjects

<http://healthcare.partners.org/phsirb/recruit.htm>

Guidelines for Advertisements for Recruiting Subjects

<http://healthcare.partners.org/phsirb/advert.htm>

Remuneration for Research Subjects

<http://healthcare.partners.org/phsirb/remun.htm>

CONSENT PROCEDURES

Explain in detail how, when, where, and by whom consent is obtained, and the timing of consent (i.e., how long subjects will be given to consider participation). For most studies involving more than minimal risk and all studies involving investigational drugs/devices, a licensed physician investigator must obtain informed consent. When subjects are to be enrolled from among the investigators' own patients, describe how the potential for coercion will be avoided.

There will be separate consent forms for Parts A, B, E, and F. Informed consent will be obtained either by the principal investigator or an experienced co-investigator prior to any participation in the study. The opportunity to talk to a licensed MD (who is readily available at the time of consent, and available overnight at the hospital) will be offered and documented in each case. After informed consent is obtained, the licensed MD will examine the subject (history and physical) to confirm whether he/she is suitable to proceed with the study. Subjects will have more than 24 hours to consider participating in the study. Prior to enrollment subjects will have all the risks of the study and details of the study procedures thoroughly reviewed. Any subject who is unable to give consent will not be studied.

NOTE: When subjects are unable to give consent due to age (minors) or impaired decision-making capacity, complete the forms for Research Involving Children as Subjects of Research and/or Research Involving Individuals with Impaired Decision-making Capacity, available on the New Submissions page on the PHRC website:

<http://healthcare.partners.org/phsirb/newapp.htm#Newapp>

For guidance, refer to the following Partners policy:

Informed Consent of Research Subjects

<http://healthcare.partners.org/phsirb/infcons.htm>

DATA AND SAFETY MONITORING

Describe the plan for monitoring the data to ensure the safety of subjects. The plan should include a brief description of (1) the safety and/or efficacy data that will be reviewed; (2) the planned frequency of review; and (3) who will be responsible for this review and for determining whether the research should be altered or stopped. Include a brief description of any stopping rules for the study, when appropriate. Depending upon the risk, size and complexity of the study, the investigator, an expert group, an independent Data and Safety Monitoring Board (DSMB) or others might be assigned primary responsibility for this monitoring activity.

NOTE: Regardless of data and safety monitoring plans by the sponsor or others, the principal investigator is ultimately responsible for protecting the rights, safety, and welfare of subjects under his/her care.

This study is primarily a physiological investigation of the factors that lead to OSA in particular individuals. Thus, subjects will be carefully monitored with physiologic instruments (airflow, oxygen saturation, end-tidal carbon dioxide, etc.) during each of the studies. During each of the physiologic measurement, subjects will be monitored by an MD (typically the PI or sometimes a co-investigator), a PhD, a co-investigator, or a trained technician very knowledgeable in Respiratory Physiology and experienced in the procedures conducted. Each of the participants will have OSA (and be otherwise healthy). The range of possible adverse events is quite narrow and will be quickly realized by the study staff and investigator(s) performing the physiologic measurement. The study staff and investigators in this protocol will meet monthly to examine raw data and discuss any difficulties encountered. Thus, the investigators involved in this study will be responsible for overseeing the integrity of the results and monitoring for adverse events. “Stopping criteria” will consist of the patient’s inability to tolerate the monitoring equipment, side effect from one of the medications, swelling of the airway, difficulty breathing, or bleeding.

Describe the plan to be followed by the Principal Investigator/study staff for review of adverse events experienced by subjects under his/her care, and when applicable, for review of sponsor safety reports and DSMB reports. Describe the plan for reporting adverse events to the sponsor and the Partners’ IRB and, when applicable, for submitting sponsor safety reports and DSMB reports to the Partners’ IRBs. When the investigator is also the sponsor of the IND/IDE, include the plan for reporting of adverse events to the FDA and, when applicable, to investigators at other sites.

NOTE: In addition to the adverse event reporting requirements of the sponsor, the principal investigator must follow the Partners Human Research Committee guidelines for Adverse Event Reporting

The Investigators and study staff will report any adverse events in accordance to the HRC guidelines to the IRB. The PI will email and call the Program Officer at the NHLBI as well as the IRB to report adverse and serious adverse events immediately when they occur.

MONITORING AND QUALITY ASSURANCE

Describe the plan to be followed by the principal investigator/study staff to monitor and assure the validity and integrity of the data and adherence to the IRB-approved protocol. Specify who will be responsible for monitoring, and the planned frequency of monitoring. For example, specify who will review the accuracy and completeness of case report form entries, source documents, and informed consent.

NOTE: Regardless of monitoring plans by the sponsor or others, the principal investigator is ultimately responsible for ensuring that the study is conducted at his/her investigative site in accordance with the IRB-approved protocol, and applicable regulations and requirements of the IRB.

The Principal Investigator has overall responsibility for Data and Safety Monitoring and Quality Assurance. The study staff will review the study and report to the principal investigator on a monthly basis to ensure adherence to the IRB-approved protocol and correct consenting procedures/documentation.

For guidance, refer to the following Partners policies:

Data and Safety Monitoring Plans and Quality Assurance

<http://healthcare.partners.org/phsirb/datasafe.htm>

Adverse Event Reporting Guidelines

http://healthcare.partners.org/phsirb/adverse_events.htm

PRIVACY AND CONFIDENTIALITY

Describe methods used to protect the privacy of subjects and maintain confidentiality of data collected. This typically includes such practices as substituting codes for names and/or medical record numbers; removing face sheets or other identifiers from completed surveys/questionnaires; proper disposal of printed computer data; limited access to study data; use of password-protected computer databases; training for research staff on the importance of confidentiality of data, and storing research records in a secure location.

NOTE: Additional measures, such as obtaining a Certificate of Confidentiality, should be considered and are strongly encouraged when the research involves the collection of sensitive data, such as sexual, criminal or illegal behaviors.

We will make every effort to maintain patient privacy and confidentiality both during and following the study. Electronic study data will be de-identified by substitution of codes for names and hospital identifiers and will be stored on a secure disk for access by co-investigators and study staff only and a hard copy will be stored in a locked cabinet. All research staff are IRB certified and it has been impressed upon them the importance of confidentiality. This study does not involve the collection of sensitive personal information from subjects. Data will be stored only at Partners sites and its use will be confined to that specified in this protocol and its approved amendments.

SENDING SPECIMENS/DATA TO RESEARCH COLLABORATORS OUTSIDE PARTNERS

Specimens or data collected by Partners investigators will be sent to research collaborators outside Partners, indicate to whom specimens/data will be sent, what information will be sent, and whether the specimens/data will contain identifiers that could be used by the outside collaborators to link the specimens/data to individual subjects.

N/A

Specifically address whether specimens/data will be stored at collaborating sites outside Partners for future use not described in the protocol. Include whether subjects can withdraw

their specimens/data, and how they would do so. When appropriate, submit documentation of IRB approval from the recipient institution.

No data or specimens will be sent to collaborators outside Partners.

RECEIVING SPECIMENS/DATA FROM RESEARCH COLLABORATORS OUTSIDE PARTNERS

When specimens or data collected by research collaborators outside Partners will be sent to Partners investigators, indicate from where the specimens/data will be obtained and whether the specimens/data will contain identifiers that could be used by Partners investigators to link the specimens/data to individual subjects. When appropriate, submit documentation of IRB approval and a copy of the IRB-approved consent form from the institution where the specimens/data were collected.

N/A

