1. **CPAP to induce flow-limitation:** After instrumentation, the patient will be asked to sleep in the supine position with the chin forward. Once asleep, CPAP will be set to the holding pressure. After several minutes of stable breathing at the holding pressure during NREM sleep, CPAP will be decreased slightly for 3-5 min in order to induce flow limitation. These maneuvers will be repeated multiple times to varying levels of suboptimal CPAP while breathing room air or while breathing the test gases for 2

consecutive respirations. If awakening occurs, the pressure will be returned to the holding pressure until stable sleep resumes.

2. **Oral devices and effect on negative effort dependence:** After instrumentation, the patient will be asked to sleep in the supine position with the chin forward in order to observe periods of spontaneous flow limitation. After a few minutes of stable sleep, the patient will be asked to wear the oral appliance or oral pressure therapy. The patient will be asked to test the oral appliance first. After a few minutes of stable sleep with oral appliance in place, the patient will be asked to change for the oral pressure therapy device.
3. **Oral appliance and effect on pharyngeal collapsibility:** The patients will be invited to participate in two additional physiological PSGs with and without OA. Those patients fitted with the temporary thermoplastic device will be asked to use it at home the night before the physiological PSG with OA. For the physiological PSGs, the instrumentation will be same described above, except the bronchoscope that will not be used. The patient will be asked to sleep in the supine position. Once asleep, CPAP will be set to the holding pressure. During the first 1-2 hours, passive upper airway collapsibility will be measured by abruptly lowering the mask pressure to subtherapeutic levels. Peak flow will be plotted against mask pressure to determine P_{crit} . During the remainder of the night, patients will be monitored with standard clinical PSG to determine sleep apnea severity (apnea-hypopnea index).

Study endpoints for Part B include successful completion of all measurements in the study, at the subject's request, or by discretion of the researcher.

Part E (expiratory flow limitation) (n=30):

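### Part B, step 2 always observes sleep without a device first, so neither device's effect on negative effort dependence can be separated from time in session

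*Protocol*

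**What the plan says.** Protocol, Research Design and Methods, Part B, step 2 (oral devices and negative effort dependence) describes one session. The patient is first asked to "sleep in the supine position with the chin forward in order to observe periods of spontaneous flow limitation". Next, "the patient will be asked to wear the oral appliance or oral pressure therapy". The order is then fixed: "The patient will be asked to test the oral appliance first". The second change comes once sleep has settled again ("After a few minutes of stable sleep with oral appliance in place"). At that point, according to step 2, "the patient will be asked to change for the oral pressure therapy device". Step 2 has no random or counterbalanced order, no return to the no-device state and no washout.

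The text is not consistent on who uses both devices. Specific Aims, Part B presents the devices as alternatives, and so does the middle sentence of step 2. The sentences after it give both in sequence.

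Aim 3 hypothesises that both devices reduce negative effort dependence and improve collapsibility. Part B lists 20 patients for this aim. Step 3 adds "two additional physiological PSGs with and without OA", for which "the instrumentation will be same described above, except the bronchoscope that will not be used". Step 3 plans Pcrit and the apnea-hypopnea index, does not state the night order, and does not include oral pressure therapy.

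The SAP covers Part F only. Part F puts its baseline and device nights in random order.

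**The concern.** Whatever changes over a session apart from the device is added to the device effect. Candidates are time asleep, the awakenings needed to fit or swap a device, and, for the second device, carry-over from the first. The protocol itself points to another: it hypothesises that topical oropharyngeal anaesthesia can induce negative effort dependence, and lidocaine is applied during instrumentation. The sites differ (nose, nasopharynx and floor of the mouth), so this makes drift plausible but does not measure it.

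At stake is the part of Aim 3 that concerns negative effort dependence. For the appliance, the step 3 nights could in principle give a supporting check. For oral pressure therapy, step 2 is the only comparison in the protocol.

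**Working it through.** **Inputs.** The order comes from Part B, step 2, and n=20 from the Part B heading (Aim 3). The documents give no SD, effect size, error rate or analysis model for this step, so there is no stated figure to reproduce. Sigma is the within-patient SD per segment. N = no device, A = appliance, P = pressure therapy.

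**Step 1: can the contrasts be estimated?** The model is outcome = patient + segment + device. With three segments it has 20 + 2 + 2 = 24 columns. With two segments and one device it has 20 + 1 + 1 = 22.

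| Order | Rank | Device versus none | A versus P |
|---|---|---|---|
| N-A-P for all 20 (as written) | 22 of 24 | not estimable | not estimable |
| N-A-P and N-P-A, 10 each | 23 of 24 | not estimable | variance 0.100 sigma² |
| All six orders (4, 4, 3, 3, 3, 3) | 24 of 24 | variance 0.101 sigma² | variance 0.100 sigma² |
| One device, N then device, 20 patients | 21 of 22 | not estimable | – |
| One device, 10 N-device and 10 device-N | 22 of 22 | variance 0.100 sigma² | – |

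Under the written order the two device columns equal the two segment columns, so the rank falls by two. If segment is left out (drift assumed zero), the variance is 2 sigma²/20 = 0.100 sigma².

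**Step 2: the one-device reading.** Suppose, as an assumption, that 10 patients use A and 10 use P, each after N. With a common segment effect the rank is 22 of 23, and device versus none is still not estimable. A versus P is now a difference between two groups' changes, with variance 2 sigma²/10 + 2 sigma²/10 = 0.400 sigma². The groups are not randomised.

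**Step 3: what drift could do (illustration only).** Assume no device effect, a drift of d sigma per segment, and a two-sided 5% paired t-test with 19 df, which the documents do not plan. For segments k apart, the noncentrality is k × d × √20/√2.

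| d | k=1: A versus N, P versus A | k=2: P versus N |
|---|---|---|
| 0 | 5% | 5% |
| 0.2 | noncentrality 0.63, 9% | noncentrality 1.26, 22% |
| 0.5 | noncentrality 1.58, 32% | noncentrality 3.16, 85% |

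The k=2 column applies only if patients use both devices in the written sequence. If they use one, every device-versus-none contrast has k=1.

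**Step 4: price of the six orders.** The effect detectable with 80% power is 0.914 sigma (36 df), against 0.909 sigma (38 df) for the written order with drift assumed zero. With two carry-over terms in the model, the device-versus-none variance is 0.124 sigma². If carry-over is not modelled, one unit from each device shifts each device-versus-none contrast by −0.32. If 4 of 20 patients lose their last segment at random (assumed; the SAP expects 20% failure in Part F), the variance is about 0.113 sigma².

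**The case against.** **Posture and sleep are controlled.** Step 2 fixes posture and asks for settled sleep before each change. This reduces drift but does not make the contrast estimable.

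**Sleep depth is recorded.** EEG, EMG, end-tidal CO₂ and airway pressure are measured in Part B, so segments could be matched or adjusted on sleep stage. Negative effort dependence is also defined relative to effort. This stands, and it makes sleep depth a weak example of uncontrolled drift. But no adjustment is planned, and unmeasured drift and carry-over would remain.

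**The rank result restates the premise.** Any single-order design with a free segment effect is rank-deficient. That is true. It shows what cannot be separated, not that bias occurs.

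**No device first protects the reference condition.** This is a real advantage, because a session may end early; the Part B endpoint text ("Study endpoints for Part B include successful completion of all measurements in the study") also allows a stop at the patient's request or the researcher's discretion. Another way to keep it is to repeat the no-device segment at the end. If drift is linear, the device-versus-none variance is then (1 + 4/9 + 1/9) sigma²/20 = 0.078 sigma². This needs a further segment and device removal, and it relies on linearity.

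**Stronger readings.** A reader might infer that every device contrast is confounded with segment whatever the text means. The documents do not support that: if each patient uses one device, appliance versus pressure therapy is a between-patient comparison with a different weakness. A reader might also take the percentages above as this study's false-positive risk, but they rest on assumed drifts and an assumed test.

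**Conclusion.** The point holds for device versus no device under any reading of step 2: the order is fixed, no device comes first, and no planned analysis repairs this. Appliance versus pressure therapy is confounded with segment and carry-over if patients use both devices in sequence, and is a non-randomised between-patient comparison if they use one.

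The loss of estimability (rank 22 of 24, or 21 of 22 with one device) assumes only that segment effects are unrestricted. The size and direction of any drift cannot be derived from the documents, so bias is possible but not shown to be large or to favour the devices.

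The scope is limited. Part B is a physiological sub-study with its own consent form. A reader might infer that the SAP's outcomes are weakened, but those belong to Part F, whose night order is random. The change is worth making because it is cheap and because step 2 is the only test of oral pressure therapy on negative effort dependence.

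**What to change.** 1. Reconcile the one-device wording in Specific Aims and step 2 with the two-device sequence in step 2, and state who uses which device.
2. For patients who use both, randomise segment order, including the position of the no-device segment. Preferably use all six orders at n=20: N-A-P and N-P-A with 4 patients each, and the other four with 3 each. For patients who use one, randomise 1:1 to none-device or device-none.
3. Include segment and recorded sleep stage in the analysis, keep patients who lose their last segment in the model, and add carry-over terms as a sensitivity analysis for patients who use both devices.
4. If the no-device segment must stay first, randomise device order, which repairs only device versus device. Describe the device-versus-none results as not separable from time in session.

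**Cost.** A randomisation list and changed wording, with no extra patients or nights and still two device changes per patient. Almost no precision is lost with complete data. Six of 20 patients would have no device last and could lose that segment if the session ends early. Carry-over does not fully cancel over the six orders. In one-device patients, one unit of carry-over would shift the effect by −0.5 and could not be separated within patients.
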